4.13. Adaptive design: possible changes after an interim analysis

An interim analysis will be conducted when approximately 60% of the planned 3-month time-intervals have been completed. The analysis results will be seen and reviewed only by the trial data safety and monitoring board (DSMB) that will advise the study team on trial continuation, according to its charter. Based on its adaptive design, the trial conduct will be altered in case the interim analysis gives either of the following results:

[figure not shown]
1. There is evidence of a mortality benefit in both of the azithromycin groups as compared to the placebo group but no statistically significant difference between the two azithromycin groups.

- a. In this scenario, the team will drop the placebo arm and re-randomize the previous placebo-clusters into either of the two azithromycin groups, at 1:1 allocation ratio. All trial participants will be informed about the change and a new consent will be requested for participation in the revised trial.
- b. Before implementation, the participant information leaflet and an amended consent form will be submitted to the appropriate ethics committees and institutional review boards (IRB) for review and approval.
- c. Subject to endorsement by the trial data safety and monitoring board (DSMB) before the onset of data collection, the team proposes to consider a mortality difference in an interim analysis statistically significant if a 2-sided p-value is smaller than 0.001 (Peto et al., 1976).
- d. After the results from the azi-quarterly and azi-biannual groups comparison are available, the team will offer to work with the Malian Ministry of Health on implementation of a public health MDA intervention in Kayes, Kita, and Koulikoro and possibly Bougouni and Segou regions of Mali, choosing the MDA regimen (quarterly or biannual) based on the trial data.

2. There is evidence of a mortality benefit in one or both of the azithromycin groups and also a statistically significant difference between the two azithromycin groups.
 - a. In this scenario, the provision of the study MDA will be stopped, and the team will offer to work with the Malian Ministry of Health on implementation of azithromycin MDA in Kayes, Kita, and Koulikoro and possibly Bougouni and Segou regions of Mali, choosing the MDA regimen (quarterly or biannual) based on the trial data.

A separate trial (SANTE) in Sikasso Region is evaluating the benefits of azithromycin provided to pregnant women and to infants at the 6-week EPI visit. The combined results of the SANTE trial and the newly proposed trial will provide important evidence for decision-making around the optimal strategy for delivering azithromycin for child survival in the whole of Mali.

The adaptive design is illustrated in Figure 4 below.

4.14. Data collection on infant morbidity

Earlier trials and other studies have suggested that azithromycin MDA might also have an impact on child morbidity. Whilst it would be difficult to assess morbidity reliably on an individual level in all LAKANA participants, we intend to collect morbidity related information among infants who live in the 60 villages selected for additional outcome assessment (secondary outcome sample). These villages are served by four health centers, where we will establish a LAKANA office and post research staff for the additional data collection.

During the normal MDA home visits in these selected villages, the LAKANA team will ask if a child has been ill in the preceding 14 days, with fever with respiratory symptoms (acute respiratory infection, ARI), fever without respiratory symptoms (proxy for malaria), diarrhea, or any other symptoms. These questions will be asked about each 4-14 month old infants and children, i.e. those who were eligible to receive the study drug intervention at an earlier MDA round.

From the collected data the team will calculate incidence of various types of illness episodes in the three study arms. The team will then calculate relative risks for the illnesses in azi-quarterly and azi-biannual groups, as compared to the control group.

4.15. Data collection on infant growth and nutritional status

A relatively recent meta-analysis suggested that antibiotic treatment of children in low-income countries might improve their linear growth (Gough et al., 2014). The review did not include enough studies on infants, so the question of antibiotic effect on infant growth is still open. It is, however, possible, that azithromycin might also promote growth in this age group (in which length and weight gain is faster than among older children), and hence it justifiable to study growth as a secondary outcome in a mortality trial.

The sub-sample will be formed from children, who reside in the 60 villages around the four selected health centers (secondary outcome sample). In these villages, data collectors will take anthropometric measurements from 6-8 and 12-14 month old children on study visits 6, 7, 8, and 9, i.e. at 15, 18, 21, and 24 months after the enrollment of the village into the trial. At these visits, the 6-8 month-old and 12-14 month old children will have received two and four doses of study drugs, respectively, unless they migrated into the village later, were absent, unlocated or declined study drug administration. Thus this sampling frame ensures maximal exposure to the study drug at size assessment.

At each time point, we expect to measure a mean of 7.5 children / village, i.e. the total sample size will be 1800 children, i.e. approximately 600 per group. This sample size will provide the study with 80% power to detect difference of approximately 0.2 SD units in anthropometric indices, which is a typical achievement in nutritional supplementation trials (Dewey and Adu-Afarwuah, 2008).

Measurements taken from the sub-sample include length, weight, and mid upper arm circumference (MUAC). Length will be assessed using a commercial length board (ShorrBoard®, WEIGH AND MEASURE, LLC, Olney, Md, USA) and recorded to the nearest 1 mm. Weight will be assessed using an electronic infant weighing scale (SECA 354) with reading increments of 10g. MUAC will be measured with non-stretchable plastic insertion tapes and the results will be recorded to the nearest 1 mm. All measurement will be done in triplicate.

The data collectors measuring anthropometrics will be trained and standardized prior to beginning of data collection, modified from the procedures used in the WHO 2006 growth standard study (WHO, 2006). Standardization sessions will be repeated every 6 mo during data collection. We will calculate weight-for-age (WAZ), length-for-age (LAZ), weight-for-length (WLZ), and arm circumference-for-age z-scores using the WHO 2006 Child Growth Standards. We will also calculate the percentage of children who are moderately or severely stunted (LAZ < -2 / -3), or moderately or severely wasted (WLZ < -2 / -3). Those with wasting will be referred for nationally recommended diagnostics and treatment.

4.16. Data collection on antimicrobial resistance

One of the major concerns in the use of azithromycin MDA is the possibility of increasing AMR, resulting in the loss of mortality benefits, and possibly even increasing health problems. As explained in chapter 3.03, macrolide resistance has earlier been observed in the treated individuals soon after azithromycin MDA, but there is relatively little data on longer follow-up or spread of AMR to unexposed populations. In LAKANA, we will therefore monitor prevalence of azithromycin resistance before, during and after the intervention and both among children receiving and those not receiving MDA with the study drugs.

To allow comparability to national and international AMR statistics, we will primarily study AMR with a traditional phenotypic culture method, isolating individual colonies of selected indicator bacteria (*S. pneumoniae* and *E. coli*) from children and assessing

bacterial growth on a Petri-dish in the presence or absence of azithromycin. To maximise comparison of these surveillance cultures with antimicrobial resistance results from other azithromycin MDA trials (such as the AVENIR trial in Niger), details of sample collection and processing methods will be harmonised between the different studies.

Studying individual colonies of selected indicator bacteria is a widely used approach for AMR assessment, but it gives no information on possible antibiotic effects on other colonies of the same species or any of the other bacterial species (some of which may be clinically much more important than the indicator bacteria). We will therefore also employ genetic methods to study microbiota composition and the presence of molecular markers of AMR in host bacteria. As sample collection for the AMR component will take three years and molecular methods are rapidly developing, we will store samples for these genetic (and possible other) analyses until the completion of data collection and choose the exact molecular methods only at that time point. Similar to the indicator bacteria analyses, these sample collection and processing for these studies will be harmonised with the AVENIR trial in Niger.

[figure not shown]
In the first phase, we will thus address the following questions:

1. What is the impact of biannual or quarterly azithromycin MDA to 1-11 month (29-364 days) old infants on the prevalence of phenotypic azithromycin resistance among *S. pneumoniae* or *E. coli* strains isolated from 4–14-month-old children, who have received 1-4 rounds of azithromycin MDA?
2. What is the impact of biannual or quarterly azithromycin MDA to 1-11 month (29-364 days) old infants on the prevalence of phenotypic azithromycin resistance among *S. pneumoniae* or *E. coli* strains isolated from 49–59-month-old children, who live in the same Malian communities but have not received azithromycin MDA?
3. What is the impact of biannual or quarterly azithromycin MDA to 1-11 month (29-364 days) old infants on the prevalence of phenotypic azithromycin resistance among *S. pneumoniae* or *E. coli* strains isolated from 15-26-month-old children, who have received 1-4 rounds of azithromycin MDA and live in a village that stopped azithromycin MDA 1 year before?
4. What is the impact of biannual or quarterly azithromycin MDA to 1-11 month (29-364 days) old infants on the prevalence of phenotypic azithromycin resistance among *S. pneumoniae* or *E. coli* strains isolated from 24-35-month-old children, who have received 1-4 rounds of azithromycin MDA 1 year before and who live in a village that continued azithromycin MDA?

To ascertain if clinical disease is being influenced by azithromycin MDA, we will also study AMR in bacteria isolated from stools with children presenting at any of the four selected health facilities because of dysentery (bloody stools) or blood, urine, or cerebrospinal fluid of 1–11-month-old infants or older children hospitalized in the nearby Kita District Hospital because of a severe, septic illness. For this purpose, we will establish a basic microbiology laboratory in this hospital and support its operations during the LAKANA trial. We have chosen Kita for this purpose, because it is the largest hospital in the Kita region and because we will establish our LAKANA biospecimen processing and storage laboratory in this hospital. Kita is also relatively near Bamako, which facilitates support and oversight by the CVD-Mali laboratories and the LAKANA research team.

diseases, and the prevalence of AMR in bacteria that are causing severe disease. This will facilitate understanding about the clinical significance of AMR, possibly caused by the MDA intervention.

For hypothesis testing on the prevalence of AMR in indicator bacteria, we will need a total of 1,350 children. These children will be identified in the 60 villages around the four health centers selected for secondary outcome data collection in Kita. All 4–14-month-old and 49–59 month old children in this sub-sample will be invited to provide biological samples for AMR analyses at enrollment (visit 1) and at 12 months (visit 5), 24 months (visit 9) and 36 months (visit 11) after the inclusion of the village into the study.

To facilitate the AMR sample collection before study drug administration, the team making home visits in this sub-sample of clusters will include a study nurse. Before any MDA, this nurse will collect one nasal and three rectal swabs from the study infants, in a tent set up in the village that is being visited.

To assess whether AMR carriage persists on an individual level we will sample children at the final time point (visit 11) who have received 1–4 MDA doses and who live in a village that stopped MDA intervention 1 year earlier (children at 15–26 month-old). Additionally, we will sample children (24–35 months old) at visit 9 (Koulikoro/Kati region) who have received 1–4 MDA doses 1 year earlier, but live in a village that continued MDA intervention.

After collection, the nasopharyngeal swabs will be placed in STGG media (skim milk, tryptone, glucose, and glycerin), one rectal swab will be placed in Cary-Blair media, the second rectal swab will be placed in DESS media (DMSO/EDTA/saturated sodium chloride) and the third rectal swab will be frozen without preservatives in a cryovial. The third rectal swabs will be flash frozen in dry shippers containing liquid nitrogen that has been absorbed in the container linings. Other samples will be placed in a +4°C cooler box. All samples will be transported within 2–4 hours to a study laboratory in Kita or to the main laboratory in Bamako, where a laboratory technician will process them and store them at -80°C: From the Kita laboratory, samples will be periodically transported to the main CVD-Mali laboratory for processing.

Nasopharyngeal swabs will be primarily cultured on chocolate agar with an optochin disc, to identify pure colonies of *Streptococcus pneumoniae*. Rectal swabs will be primarily cultured on MacConkey plates, to identify pure clones of *Escherichia coli*. Isolated colonies will then undergo phenotypic AMR analysis with bacterial culture on Petri-dishes supplied with Azithromycin containing antibiotic strips (E-test).

In the first phase, we will determine azithromycin sensitivity from all the samples collected from 4–14-month-olds at 24 months and from 49–59 month olds at 36 months (n = 1,350 per time point and age group) and from 1/3 of the samples at the other time-point (for descriptive purposes, not for hypothesis testing). We will also determine azithromycin sensitivity from samples collected from 15–26-month-olds at 36 months (Kita region) and 24–35-month-olds at 24 months (tertiary AMR samples). We will then calculate AMR prevalence for in *S. pneumoniae* and *E. coli*, for each of the time points and each of the three trial arms separately. At each time point, we will calculate the

difference (95% confidence interval, CI) in AMR prevalence between the control and azi-biannual clusters on one hand and between the control and azi-quarterly clusters on the other. The pre-set non-inferiority margin is 10 %-points, i.e. if the entire 95%CI of the difference in less than 10%-points, the data will be considered supportive of the non-inferiority hypothesis.

The 10% non-inferiority margin has been obtained by a DELPHI method talking to many infectious disease specialists – and also used in the WHO coordinated ABCD trial. The margin is expressed as an absolute and not a relative difference in AMR prevalence, because absolute increase in AMR prevalence will indicate how many additional possible exposures with resistant bacteria the study area population may face. Thus, an increase from 1% to 11% or 50% to 60% will provide 10 new “risk” persons in a group of hundred even if one goes up in relative terms by 1000% and the other only 20%.

We will retain and freeze at -80°C the original swabs after plating as well as the identified bacterial colonies, to allow further analyses with the indicator bacteria or any other intestinal bacteria or other microbes with later evolving methods. Bacterial colonies will be stored at two points for later analyses: during primary culture when organisms other than the main targets are grown and from the antibiotic sensitivity plate in order to capture resistance diversity within the target organisms. The stored cultures can subsequently be analysed through standard culture or by molecular techniques.

Figure 6 summarises samples taken for AMR analyses and stored at -80°C. In total, there will be an estimated of 54,000 vials, without the so called “clinical isolates”, taken from ill children. In total, these stored samples thus will fill one -80°C freezer.

Duration of intervention in community	Child age	# of given MDA rounds / village	Biological specimen	Storage media	Estimated # of aliquots	Volume / aliquot	Storage temperature	# of children
0 months	4-14 mo & 49-59 mo	0	Nasopharyngeal swab	STGG media	2	100 ug	-80°	1350 + 1350
0 months	4-14 mo & 49-59 mo	0	Rectal swab	Cary-Blair media	1	100 ug	-80°	1350 + 1350
0 months	4-14 mo & 49-59 mo	0	Rectal swab	DESS Media	1	100 ug	-80°	1350 + 1350
0 months	4-14 mo & 49-59 mo	0	Rectal swab	None, stored dry	1	100 ug	-80°	1350 + 1350
12 months	4-14 mo & 49-59 mo	2	Nasopharyngeal swab	STGG media	2	100 ug	-80°	1350 + 1350
12 months	4-14 mo & 49-59 mo	2	Rectal swab	Cary-Blair media	1	100 ug	-80°	1350 + 1350
12 months	4-14 mo & 49-59 mo	2	Rectal swab	DESS Media	1	100 ug	-80°	1350 + 1350
12 months	4-14 mo & 49-59 mo	2	Rectal swab	None, stored dry	1	100 ug	-80°	1350 + 1350
24 months	4-14 mo & 49-59 mo	6	Nasopharyngeal swab	STGG media	2	100 ug	-80°	1350 + 1350
24 months	4-14 mo & 49-59 mo	6	Rectal swab	Cary-Blair media	1	100 ug	-80°	1350 + 1350
24 months	4-14 mo & 49-59 mo	6	Rectal swab	DESS Media	1	100 ug	-80°	1350 + 1350
24 months	4-14 mo & 49-59 mo	6	Rectal swab	None, stored dry	1	100 ug	-80°	1350 + 1350
12 months post-intervention	4-14 mo & 49-59 mo	0	Nasopharyngeal swab	STGG media	2	100 ug	-80°	1350 + 1350
12 months post-intervention	4-14 mo & 49-59 mo	0	Rectal swab	Cary-Blair media	1	100 ug	-80°	1350 + 1350
12 months post-intervention	4-14 mo & 49-59 mo	0	Rectal swab	DESS Media	1	100 ug	-80°	1350 + 1350
12 months post-intervention	4-14 mo & 49-59 mo	0	Rectal swab	None, stored dry	1	100 ug	-80°	1350 + 1350
12-month post intervention	15-26 mo	0	Nasopharyngeal swap	STGG media	2	100ug	-80°	1000
12-month post intervention	15-26 mo	0	Rectal swab	Cairy-Blair media	1	100ug	-80°	1000
12-month post intervention	15-26 mo	0	Rectal swab	DESS Media	1	100ug	-80°	1000
12-month post intervention	15-26 mo	0	Rectal swab	None, dry swab	1	100ug	-80°	1000
12-month post treatment (in villages with MDA)	24-35 mo	0	Nasopharyngeal swap	STGG media	2	100ug	-80°	600
12-month post treatment (in villages with MDA)	24-35 mo	0	Rectal swab	Cairy-Blair media	1	100ug	-80°	600
12-month post treatment (in villages with MDA)	24-35 mo	0	Rectal swab	DESS Media	1	100ug	-80°	600
12-month post treatment (in villages with MDA)	24-35 mo	0	Rectal swab	None, dry swab	1	100ug	-80°	600

To gain a standardized understanding of antibiotics utilized for common clinical syndromes in the study area, we will collect and analyse national and regional guidelines and protocols on antibiotic prescribing on an annual basis. We also aim to monitor the amount of common antibiotics sent out to health facilities from the six study districts. A

more detailed review of antibiotic prescription will be done in the four health facilities in which the AMR sample collection takes place.

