4.07. Outcome variables

Primary efficacy outcome:

1. Mortality (deaths / 1000 years at risk) among children who were 1–11 month (29–364 days) old at the time of study drug administration.

2. As an exploratory analysis, we will assess the following factors as potential effect modifiers to the azithromycin impact on mortality among the 1–11-month (29–364 days) olds
 - a. Infant age at the time of MDA (1–5 months vs 6–11 months)
 - b. Infant weight-for-age, length-for-age, weight-for-length at the time of MDA
 - c. Infant sex
 - d. Season of MDA dosing (malaria versus non malaria season) and SMC implementation in village (SMC given versus SMC not given)
 - e. Cluster level coverage of SMC
 - f. Cluster level baseline mortality (established at first census)
 - g. Cluster and individual level coverage and number of administered azithromycin MDA doses
 - h. District of residence
 - i. Distance from the nearest health facility
 - j. Household asset or income index
 - k. Household WASH index
 - l. National outreach strategy category (standard/advanced)
 - m. Hard-to-reach village status assessed by the field workers

Secondary efficacy outcomes:

1. Prevalence of diarrhea, ARI, malaria, or other illnesses in the 14-day period before MDA visits
2. Mean weight-for age, length for age, weight-for-length, and mid upper arm circumference, and prevalence of moderate to severe stunting ($LAZ < -2$ / $LAZ < -3$) and moderate to severe wasting ($WLZ < -2$ / $WLZ < -3$) at 6–8 and 12–14 months of age.
3. Mortality (deaths / 1000 years at risk) among children who were 12–59-month-old when the latest azithromycin MDA took place in their village of residence.
 - a. This will be analyzed since azithromycin MDA could elicit herd protection that could theoretically extend beyond the actual recipient population of the treatment.

Outcomes related to antimicrobial resistance:

1. Phenotypic macrolide resistance among *E. coli* strains isolated from stool samples or *S. pneumoniae* strains isolated from nasopharyngeal swabs among 4–14-month-old children, at one year after the MDA intervention has stopped (36 months after baseline).
 - a. As descriptive information, we will provide the same information from a smaller group of children at baseline and when the intervention has continued for 12 and 24 months (i.e., after 4 or 8 rounds of MDA).

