 - b. For all isolates of azithromycin resistant *E. coli* or *S. pneumoniae*, we will also determine of phenotypic AMR against other antibiotics categorized by the World Health Organization (WHO) into "Access" group and/or that may have overlapping mechanisms: meropenem, ceftriaxone, ciprofloxacin, ampicillin, co-trimoxazole, and gentamicin for *E. coli*, and oxacillin, erythromycin, vancomycin, ciprofloxacin, ampicillin, co-trimoxazole for *S. pneumoniae*.

2. Phenotypic macrolide resistance among *E. coli* strains isolated from stool samples or *S. pneumoniae* strains isolated from nasopharyngeal swabs among 49–59-month-old children, at 24 months after cluster enrollment to the trial, i.e. when the intervention has continued for 24 months (after 8 rounds of MDA).
 - a. As descriptive information, we will provide the same information from a smaller group of children at baseline, at 12 months after enrolment (4 rounds of MDA), and at one year after the MDA intervention has stopped
 - b. In here, we are primarily interested in the older age-group, since earlier research suggests that AMR prevalence will increase among the treated individuals, but we expect AMR not to spread to non-treated individuals.
 - c. In a two-year MDA and follow-up period, 49–59-month-old children will never have received any azithromycin as part of the trial.
 - d. For all isolates of azithromycin resistant *E. coli* or *S. pneumoniae*, we will also determine of phenotypic AMR against other antibiotics categorized by the World Health Organization (WHO) into "Access" group and/or that may have overlapping mechanisms: meropenem, ceftriaxone, ciprofloxacin, ampicillin, co-trimoxazole, and gentamicin for *E. coli*, and oxacillin, erythromycin, vancomycin, ciprofloxacin, ampicillin, co-trimoxazole for *S. pneumoniae*.
3. Genetic markers of azithromycin and other antibiotic resistance (resistome) of intestinal and nasopharyngeal microbiota among 4–14-month-old children, at one year after the MDA intervention has stopped.
 - a. As descriptive information, we will provide the same information from a smaller group of children at baseline and when the intervention has continued for 12 and 24 months.
 - b. We are primarily interested in the post-intervention situation, since earlier research suggests that AMR prevalence will increase among the treated individuals soon after azithromycin treatment, but we expect the prevalence to go down after the intervention.

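### Section 4.16 puts the full resistance-testing sample in the opposite age and time cells from 4.07 and 5.04, leaving the first-phase tests of hypotheses 7 and 8 with 450 children each instead of 1,350

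*Combined protocol and SAP*

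**What the plan says.** **Section 4.16.** Both age groups are swabbed "at enrollment (visit 1) and at 12 months (visit 5), 24 months (visit 9) and 36 months (visit 11"). The stated requirement is: "For hypothesis testing on the prevalence of AMR in indicator bacteria, we will need a total of 1,350 children". The laboratory rule for the first phase is that "we will determine azithromycin sensitivity from all the samples collected from 4–14-month-olds at 24 months and from 49–59 month olds at 36 months", with 1,350 per time point and age group. Azithromycin sensitivity is otherwise determined "from 1/3 of the samples at the other time-point (for descriptive purposes, not for hypothesis testing"). The same section then computes arm differences at every time point and applies the 10-point margin without singling one out.

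**Section 4.07.** AMR outcome 1 is phenotypic resistance "among 4–14-month-old children, at one year after the MDA intervention has stopped (36 months after baseline"). Its descriptive companion comes "from a smaller group of children at baseline and when the intervention has continued for 12 and 24 months". AMR outcome 2 is phenotypic resistance "among 49–59-month-old children, at 24 months after cluster enrollment to the trial", with descriptive data "at baseline, at 12 months after enrolment (4 rounds of MDA), and at one year after the MDA intervention has stopped".

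**Section 5.04.** The 1,350 are tested in 4–14-month-olds 12 months after the intervention stops and in 49–59-month-olds after eight rounds. The three other time points have 450 each, and the total is 5,400 analyses per organism.

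**Section 5.02.** The non-inferiority rule names no time point.

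**The concern.** The two cells that 4.16 tests in full are the two that 4.07 treats as descriptive, and the two that 4.07 and 5.04 reserve for the outcome receive one third in 4.16. The 4.16 paragraph is the instruction a laboratory would follow. If it is followed, both main phenotypic tests rest on 450 children each, in cells that 4.16 itself labels as not for testing.

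For 4–14-month-olds there is a further cost. Hypothesis 7 is that there is no sustained increase. The full sample would fall at 24 months, when 4.16 expects resistance to be raised, and not one year after stopping, where the claim has to be shown.

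Conflicting time points also leave room to choose the confirmatory comparison after the results are seen, because neither 4.16 nor 5.02 ties the margin to one cell per age group.

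**Working it through.** **1. Timings side by side**

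| Source | 4–14 months | 49–59 months |
|---|---|---|
| 4.16, laboratory rule | 24 months | 36 months |
| 4.07, AMR outcomes 1 and 2 | 36 months | 24 months |
| 5.04, full sample | 12 months after stopping | after 8 rounds |
| 5.01, hypotheses 7a and 8a | 12 months after stopping | 12–18 months of intervention |
| 4.16, stated hypotheses | one year after the intervention | at any time, peak 12–24 months |
| 4.02, questions 2.1 and 2.2 | one year after stopping | during and after the intervention |
| 4.16, question 1 | children already given 1–4 rounds, no date | – |

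For the younger group every dated statement except the laboratory rule gives one year after stopping. For the older group the timings vary, but no outcome or hypothesis singles out 36 months.

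**2. Reproducing the plan's count**

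1,350 / 3 = 450, and 2 age groups × (1,350 + 3 × 450) = 5,400, as in 5.04. The total is the same under either assignment, so it cannot reveal the exchange.

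**3. Power at 1,350 and at 450**

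Inputs from 5.04: control prevalence p = 12% (E. coli) and 6% (S. pneumoniae); recovery 95% and 65%; between-cluster coefficient of variation k = 0.3; margin 0.10; one-sided 2.5%; 60 clusters. Assumed: true difference 0. The sub-sample allocation is not stated outright, so equal arms and 3:4:2 (control : biannual : quarterly) are both shown.

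- ICC = k²p/(1−p): 0.0123 for E. coli, 0.0057 for S. pneumoniae
- m = N × recovery / 60, and DEFF = 1 + (m−1) × ICC
- SE = √[p(1−p)(1/n_c + 1/n_t) × DEFF], with n_c and n_t the isolates in the control and azithromycin arms
- Power = Φ(0.10/SE − 1.96)

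E. coli, equal arms, N = 450: 450/3 × 0.95 = 142.5 isolates per arm; m = 7.125; DEFF = 1.075; SE = √(0.1056 × 2/142.5 × 1.075) = 0.0399; power = Φ(2.505 − 1.96) = 71%. At N = 1,350: 427.5 isolates per arm; DEFF = 1.250; SE = 0.0249; power 98%.

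| | N = 1,350 | N = 450 |
|---|---|---|
| E. coli, equal arms | 98% | 71% |
| E. coli, quarterly vs control, 3:4:2 | 95% | 61% |
| E. coli, biannual vs control, 3:4:2 | 99% | 76% |
| S. pneumoniae, equal arms | over 99% | 83% |
| S. pneumoniae, quarterly vs control, 3:4:2 | 99% | 74% |
| S. pneumoniae, biannual vs control, 3:4:2 | over 99% | 87.5% |

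The largest observed E. coli difference that still passes is 10 points minus the 95% CI half-width. With equal arms it falls from 10 − 4.87 = 5.1 points to 10 − 7.82 = 2.2 points.

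Section 5.04 describes the 450 as coming from twenty clusters per arm, which is read here as 60 in total. If it means 20 clusters in total, E. coli power at 450 is 64% with equal arms, and 55% (quarterly) and 70% (biannual) at 3:4:2. S. pneumoniae is then 72–86%.

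**4. The plan's 80%**

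For E. coli with equal arms, n per arm = 2 × 0.12 × 0.88 × (1.96 + 0.84)² / 0.10² gives 166. Then 166 × 1.25 / 0.95 gives 219 children per arm, or 657 in total. On these inputs 1,350 gives more than 80% power, and 450 falls short for E. coli.

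**The case against.** Four points can be made for the plan.

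- **Section 4.16 partly supports its own 24-month choice.** Its question 1 concerns 4–14-month-olds who have had 1–4 rounds. The last dosing visit is visit 8, at month 21, and the minimum age for dosing is 29 days. A 4–14-month-old at month 36 was born after that visit or too shortly before it to be eligible, so question 1 can be answered only during the intervention or shortly after it. This stands: a pure slip is not the only reading, and moving the full sample to 36 months leaves question 1 with one-third samples. It does not explain the older group's 36 months, nor displace 4.07 and 5.04.
- **For the older group, 36 months is within the broad question.** Question 2.2 and the any-time wording in 4.16 both cover it. This stands, so a reader should not infer that testing at 36 months is irrelevant. What is missing is any outcome or hypothesis that makes it the main test point.
- **Nothing is lost.** The rule covers only the first phase, and both age groups' swabs are taken at all four visits and frozen. A reader might infer that hypotheses 7 and 8 could no longer be tested properly. The documents do not support that; stored samples can make up the shortfall. Extra testing added after results are known would, however, look data-driven.
- **The power loss is uneven.** With 60 clusters, S. pneumoniae at 450 falls below 80% only for quarterly versus control at 3:4:2. It would be wrong to say that both organisms lose adequate power throughout.

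**Conclusion.** The plan is wrong as written. The laboratory rule in 4.16 reverses the full-sample cells of 4.07 and 5.04, and following it gives the first-phase tests of hypotheses 7 and 8 one third of the intended children.

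The contradiction and the drop from 1,350 to 450 follow from the text alone. The power figures rest on the 5.04 inputs, a true difference of zero, 60 clusters and the allocation shown. For E. coli every allocation examined falls below the planned 80%; for S. pneumoniae the result depends on the allocation.

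The error should be corrected before testing follows the rule, but it is recoverable. Hypotheses 10 and 11, on the 15–26- and 24–35-month-olds, are not affected.

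**What to change.** - **4.16, laboratory rule:** test all 4–14-month-old samples at 36 months (visit 11), all 49–59-month-old samples at 24 months (visit 9), and one third at the other times.
- **4.16 and 5.02, non-inferiority rule:** state that the 10-point conclusion for hypotheses 7 and 8 is drawn at these two time points, and that differences at other times are descriptive.
- **5.01, hypothesis 8a:** change to 24 months.
- **4.16, older-group hypothesis:** reconcile the any-time wording with a single confirmatory test at 24 months.
- **4.16, question 1:** state that it is answered descriptively, from the one-third samples taken during the intervention.

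Two smaller alignments are separate from this point. Hypothesis 9a (resistance genes, 12–18 months) differs from 4.07 AMR outcome 3 (one year after stopping). The AMR risk ratios in 5.02 are listed at 12 and 24 months only, and 36 months should be added.

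The cost is wording. No visit or sample is added, and assays stay at 5,400 per organism.
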